8.1.5.2.1 Treatment-Emergent Adverse Events (TEAE)

AEs will be coded using MedDRA. A TEAE is defined as AE that began or worsened in severity after initiation of study drug.

AEs starting more than 30 days following the last dose of study drug will not be included in summaries of TEAEs. For subjects who continued into Period 2, AEs that are reported in Period 2 will be captured in the combined safety analysis of Period 1 and Period 2.

As a general safety summary, the number and percentage of subjects experiencing TEAEs will be summarized for each treatment group for the following AE categories:

- All AEs;
- All severe AEs;
- All reasonably possibly related AEs;
- All SAEs;
- Frequent AEs (reported in 2% of subjects or more in any treatment group);
- Frequent reasonably possibly related AEs (reported in 2% of subjects or more in any treatment group);
- Discontinuations due to AEs;
- Death.

Additional AEs may be considered for tabulation/summary based on recommendations from Clinical and Safety as deemed appropriate.

TEAEs will be summarized and presented by system organ classes (SOCs) and preferred terms (PTs) using MedDRA. The SOCs will be presented in alphabetical order, and the PTs will be presented in alphabetical order within each SOC.

TEAE will also be summarized by maximum severity and by maximum relationship.

The AEs of special interest (including but not limited to serious infection, opportunistic infection, herpes zoster, TB, gastrointestinal perforations, malignancies, MACE, renal dysfunction, anemia, increased CPK, non-cardiac, non-CNS embolic and thrombotic events, and drug-related hepatic disorders) will be summarized. Event rate (per 100 patient years) for AEs of special interest will also be summarized for the combined safety analysis of Period 1 and Period 2.

All AEs leading to discontinuation of study drug will be presented in listing format. A listing by treatment group of TEAEs grouped by SOC and MedDRA preferred term with subject identification numbers will be generated.

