## **8.0 Study Drug Exposure and Compliance**

### **8.1 Study Drug Exposure**

The duration of exposure to study drug will be summarized for the safety analysis set by the following groups.

1. Placebo

2. Upadacitinib 15 mg QD

This includes upadacitinib 15 mg QD exposure from subjects starting on upadacitinib 15 mg QD and subjects switching from placebo to upadacitinib 15 mg QD.

3. Upadacitinib 30 mg QD

This includes upadacitinib 30 mg QD exposure from subjects starting on upadacitinib 30 mg QD and subjects switching from placebo to upadacitinib 30 mg QD. Exposure is censored at time of dose switch from upadacitinib 30 mg QD to upadacitinib 15 mg QD.

4. upadacitinib 15 mg QD switched from upadacitinib 30 mg QD

This includes upadacitinib 15 mg QD exposure from subjects who switched dose from upadacitinib 30 mg QD to upadacitinib 15 mg QD.

Starting with Amendment 6, all subjects will receive open-label upadacitinib 15 mg QD, including those currently on upadacitinib 30 mg QD. Exposure to upadacitinib 30 mg QD (Group 3) will be censored prior to the day subject received the first dose of upadacitinib 15 mg QD, and subsequent exposure to upadacitinib 15 mg QD will be summarized under a separate group (Group 4).

The duration of exposure to study drug will be summarized for each group as specified above, with the number of subjects, mean, standard deviation, median, minimum and maximum values. In addition, the number and percentage of subjects exposed to study drug will be summarized for the following cumulative duration intervals.

- $\geq 2$  weeks
- $\geq 1$  month
- $\geq 3$  months
- $\geq 6$  months

- $\geq 9$  months
- $\geq 12$  months
- $\geq 18$  months
- $\geq 2$  years
- $\geq 2.5$  years
- $\geq 3$  years
- $\geq 4$  years

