#### 10.2.1.1 Adverse Events Overview

The number and percentage of subjects experiencing TEAEs will be summarized by "as treated" treatment group and overall for the following AE categories.

- All TEAEs
- Treatment-emergent serious adverse events (SAEs)
- Treatment-emergent severe adverse events
- TEAEs reasonably possibly related to study drug
- TEAEs of special interest
- TEAEs leading to discontinuation of study drug
- TEAE leading to death

In the AE overview summary, any event with an unknown severity will be considered as severe and any AE with an unknown relationship will be considered as having "reasonable possibility" of being related to study drug.

Additional AEs may be considered for tabulation/summary based on recommendations from Clinical and Safety as deemed appropriate.

For TEAEs of special interest, the point estimate and 95% CI (using normal approximation) will be provided for the treatment difference in AE percentage between each upadacitinib dose group and the combined placebo group.

As a sensitivity analysis, the AE overview summary will be repeated by randomized treatment groups (upadacitinib 15 mg QD, upadacitinib 30 mg QD and the combined placebo groups). In this summary, all AEs with an onset date after the first dose of study drug will be included, regardless of whether the AE occurred more than 30 days after the last dose of study drug.

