## **10.2.2 Analysis of Long-Term Adverse Event Rates**

Long-term adverse event rates will be analyzed using event rates adjusted by cumulative exposure and will be based on the actual treatment received at the time of AE occurrence. Starting with Amendment 6, all subjects will receive open-label upadacitinib 15 mg QD, including those currently on upadacitinib 30 mg QD. For subjects who previously received upadacitinib 30 mg QD, adverse events and exposure to upadacitinib 30 mg QD will be censored at the time of dose switch; subsequent adverse events and exposure starting the day of first dose of upadacitinib 15 mg QD will be summarized under a separate group.

The detailed treatment groups, including the handling of dose switch, are defined in Section [8.1](#).

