### **10.2.2.1 Overview of Adverse Events Rates per 100 Patient-Years of Study Drug Exposure**

An overview of AEs per 100 patient-years of study exposure will be presented by treatment group and overall for the following AE categories.

- All TEAEs
- Treatment-emergent serious adverse events (SAEs)
- Treatment-emergent severe adverse events
- TEAEs reasonably possibly related to study drug
- TEAEs of special interest
- TEAEs leading to discontinuation of study drug
- TEAE leading to death

For this calculation, 1 year will be considered to be 365.25 days. For each treatment group, the numerator of the overall rate will be the total number of TEAEs reported for

the event; that is, a subject can contribute more than one event to the numerator. For each treatment group, the denominator of the rates will be the total number of days exposed to study drug summed across all treated subjects divided by 365.25. Please refer to Section 6.0 for the calculation of study drug exposure. The AE rate per 100 patient-years of exposure will be calculated as  $(\text{[numerator/denominator]}) \times 100$ . The number of AEs reported (numerator), the total number of years of study drug exposure (denominator), and the AE rate per 100 patient-years will be presented for each treatment group and overall.

In the AE overview summary, any event with an unknown severity will be considered as severe and any AE with an unknown relationship will be considered as having "reasonable possibility" of being related to study drug.

Additional AEs may be considered for tabulation/summary based on recommendations from Clinical and Safety as deemed appropriate.

For TEAEs of special interest, the point estimate and 95% CI (using normal approximation) will be provided for the treatment difference in AE rate per 100 patient-years between each upadacitinib dose group and the combined placebo group.

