### **10.2.2.3 Adverse Events of Special Interest Rates per 100 Patient-Years of Study Drug Exposure**

The Adverse Events of Special Interest (AESI) categories will be summarized and presented for each treatment group and overall using SOC and MedDRA PT. The AESI categories will be identified as defined in Table 8. Adjudicated cardiovascular events will be summarized and presented by treatment group using the CAC adjudicated categories.

For each treatment group, the Adverse Events of Special Interest (AESI) rate per 100 patient-years of exposure will be calculated overall, for each SOC and each PT, for each of the AESI listed in Section 10.2.1.6.

For this calculation, 1 year will be considered to be 365.25 days. For each treatment group, the numerator of the overall rate, the SOC rate, or the PT rate, will be the total number of TEAEs reported overall, for the SOC, or for the PT, respectively; that is a subject can be counted more than once overall, for a SOC, and for a PT. For each treatment group, the denominator of the rates will be the total number of days exposed to study drug summed across all treated subjects divided by 365.25. Please refer to Section 6.0 for the calculation of study drug exposure. The AE rate per 100 patient-years of exposure will be calculated as  $[(\text{numerator}/\text{denominator})]*100$ . The number of AEs

reported (numerator), the total number of years of study drug exposure (denominator), and the AE rate per 100 patient-years will be presented overall, for each SOC, and for each PT for each treatment group.

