## 11.0 Summary of Changes

### 11.1 Summary of Changes between the Previous Version and the Current Version

The primary efficacy analysis and Period 1 reporting have been completed under the SAP version 2.0. The current SAP update applies only to future reporting of long-term analysis.

1. Updated throughout the SAP to align with Protocol Amendment 6, 7, and 8 including handling of dose switch from upadacitinib 30 mg QD to 15 mg QD (hereafter referred to as "dose switch") and change of study length from up to 5 years to 260 weeks. Updated throughout the SAP to replace "ABT-494" with "upadacitinib."
2. Updated Section 7.0. To clarify analysis details and incorporate additional summary of dose switch.
3. Updated Section 8.1. Study drug exposure groups to accommodate dose switch.
4. Updated Section 9.1.1 and Section 9.3. To incorporate handling of dose switch for long-term efficacy analysis.
5. Updated Section 9.1.2. To describe the missing data handling approach for the additional sensitivity analysis using longitudinal models for long-term efficacy.
6. Updated Section 9.3. To incorporate the additional sensitivity analysis for long-term efficacy.
7. Added language to clarify analysis details in Section 10.2.1.1, Section 10.2.1.6, Section 10.2.2.1, Section 10.2.2.3, Section 10.3.3.2, and Section 10.4.3.
8. Updated Section 10.2.1.6, and Section 10.4.1. To align with the latest upadacitinib AESI definitions in PSSAP V4.0.

9. Updated Section 10.1., Section 10.2.2, Section 10.3.3.1 Section 10.3.3.2 Section 10.3.3.3 and Section 10.4.3 to incorporate handling of dose switch for long-term safety analysis.
10. Added Appendix B to describe analysis accounting for impact of COVID-19 pandemic.
11. Added Section 11.0 for summary of changes and Section 12.0 for SAP version history summary.

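### The long-term AESI rate difference compares up to 260 weeks of upadacitinib with at most 12 weeks (46 patient-years) of placebo: it is confounded with time, and its normal-approximation CI fails when placebo events are few or zero

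*SAP*

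**What the plan says.** SAP 10.2.2 says that long-term AE rates "will be based on the actual treatment received at the time of AE occurrence", using the exposure groups of SAP 8.1. There, the 15 mg group combines subjects who start on 15 mg with "subjects switching from placebo to upadacitinib 15 mg QD". The 30 mg group is built the same way and is censored at the switch to 15 mg. Under SAP 4.2 all placebo subjects move to upadacitinib after Week 12, and the Protocol synopsis gives 260 weeks of treatment in total.

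For AESIs, SAP 10.2.2.1 then asks for a point estimate and a normal-approximation 95% CI for "the treatment difference in AE rate per 100 patient-years between each upadacitinib dose group and the combined placebo group". The numerator counts events: "that is, a subject can contribute more than one event to the numerator". No variance estimator is named. Nothing limits the contrast to Weeks 0-12, adjusts it for time, or covers sparse counts.

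Three other places bear on this:
- SAP 10.2.2.3, the section on individual AESIs, asks for rates "for each SOC and each PT, for each of the AESI listed in Section 10.2.1.6" and no placebo difference.
- SAP 10.2.1.1 already plans, for Period 1, the "treatment difference in AE percentage between each upadacitinib dose group and the combined placebo group".
- Protocol 8.1.5.2.1 commits to less: "Event rate (per 100 patient years) for AEs of special interest will also be summarized for the combined safety analysis".

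**The concern.** There are two separate problems.

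**Design.** Placebo contributes only the first 12 weeks on study. Upadacitinib contributes those weeks plus years of later follow-up, part of it during the COVID-19 pandemic, when all subjects were already in Period 2 (SAP Appendix B). Former placebo subjects supply person-time to both sides. The difference mixes drug effect with time on study and calendar time. It is unbiased for a drug effect only if AESI rates are constant over time, which the SAP neither states nor checks.

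**Interval.** With so little placebo exposure, a single AESI may well have no placebo events. A Wald interval then has no placebo variance and reflects upadacitinib variability alone.

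This is the only long-term AESI contrast with placebo that carries a CI. If the interval excludes zero, it will be taken as a finding of harm or of safety.

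**Working it through.** The documents state no patient-years, AESI rates or interval performance for this contrast, so there is no plan figure to reproduce.

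**Inputs from the documents**
- Placebo: 100 + 100 = 200 subjects for 12 weeks = 84 days (SAP 4.2).
- 15 mg: 200 starters for up to 260 weeks and 100 former placebo subjects for up to 248 weeks (SAP 4.2, 8.1; Protocol synopsis).
- One year = 365.25 days (SAP 10.2.2.1).

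**Assumptions.** Observed upadacitinib exposure of 1,000 to 1,200 PY, a range of true rates, Poisson counts, and the Wald reading of the normal approximation.

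**Exposure**
- Placebo maximum: 200 × 84 / 365.25 = 46.0 PY.
- 15 mg ceiling: (200 × 260 + 100 × 248) × 7 / 365.25 = 1,472 PY, about 32 times placebo.

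**Interval.** With u events in Tu PY on upadacitinib and p events in Tp PY on placebo, the CI is u/Tu − p/Tp ± 1.96 × √(u/Tu² + p/Tp²). I enumerated independent Poisson counts at equal true rates and summed the probability that the lower limit exceeds zero (false harm, nominal 2.5%). P(0) = exp(−rate × 46.0 / 100).

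| True rate per 100 PY | Expected placebo events | P(0 placebo events) | False harm, 1,000 to 1,200 PY | False harm, 500 PY |
|---|---|---|---|---|
| 0.3 | 0.14 | 87% | 31-42% | 6% |
| 0.5 | 0.23 | 79% | 58-67% | 19% |
| 1 | 0.46 | 63% | 62-63% | 46% |
| 2 | 0.92 | 40% | 40% | 39% |
| 3 | 1.38 | 25% | 25% | 25% |
| 5 | 2.30 | 10% | 10% | 11% |
| 10 | 4.60 | 1% | 8% | 8% |
| 20 | 9.20 | 0.01% | 6% | 6% |
| 30 | 13.8 | <0.01% | 5% | 5% |

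At 0.1 per 100 PY, false harm is 2-3% with 1,000 to 1,200 PY. False benefit is about 1% or less throughout. The 500 PY column allows for a shorter-exposed group such as 30 mg.

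**Zero placebo events**
- Wald excludes zero once u − 1.96√u > 0. At u = 3 this is −0.39; at u = 4 it is +0.08. Four events are enough: 4 in 1,000 PY gives 0.40 per 100 PY (CI 0.01 to 0.79).
- An exact conditional comparison needs (Tu/(Tu + Tp))^u ≤ 0.025, that is 83 events in 1,000 PY or 99 in 1,200 PY.
- The exact upper 95% limit for 0 events in 46.0 PY is −ln(0.025)/46.0 = 8.0 per 100 PY. The Wald interval treats that uncertainty as nil.

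**Time trend alone, with no drug effect.** Placebo rate = early. Upadacitinib rate = (46 × early + (Tu − 46) × late)/Tu. The rates are illustrative and apply to one pooled row.
- 10 per 100 PY in Weeks 0-12 and 20 later: expected difference about +9.6; false harm 53-54%.
- 30 early and 15 later: about −14.4; false benefit about 38%.
- 10 early and 12 later: about +1.9; false harm about 15%, of which 8% is present with no trend.

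**Repeat events.** Counting several events per subject usually adds variance beyond Poisson, so a Poisson-based interval would tend to be too narrow for that reason as well.

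**The case against.** The strongest reply is that the interval problem depends on how the sentence is read. SAP 10.2.2.1 is an overview in which AESIs form one category, and SAP 10.2.2.3 gives rates only for individual AESIs. One pooled row is therefore the more natural reading. Table 8 puts anaemia, CPK elevation, hepatic disorder and serious infections into that row, so zero placebo events would be unlikely and false harm would be 5 to 8%. That stands, and so the large CI error is claimed only for the per-AESI reading. The SAP should say which reading it intends.

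The Wald variance, the AESI rates and the exposure are indeed assumptions. Shorter 30 mg exposure lowers the figures at rates of 1 per 100 PY and below, but hardly changes them from 2 upwards. The two main time-trend examples are strong ones; a milder trend does less, and a constant rate gives no bias.

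The entry is also descriptive: it has no p-value, counts and patient-years appear beside it, and a SAP may add to what its protocol promises. All true, and this limits the severity. But the counts beside the interval do not tell the reader that the two groups come from different periods, or that the interval may omit placebo uncertainty. None of these points makes the comparison concurrent.

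**Conclusion.** The concern holds, as something that should be fixed and not as a threat to the trial's main conclusions. The non-concurrent, non-randomised comparison follows directly from the documents and applies to the pooled and per-AESI readings and to both doses. The imbalance is smaller for 30 mg because its exposure stops at the dose switch. The direction and size of the time bias are unknown.

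The interval error rests on the Wald reading and on assumed rates and exposure. At 1,000 to 1,200 PY, false harm is 25 to 67% against a nominal 2.5% for single AESIs at 0.3 to 3 per 100 PY. For a pooled row at 10 to 30 per 100 PY it is about 5 to 8%. A better interval would repair the second defect but not the first.

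**What to change.** Delete the long-term upadacitinib-minus-placebo difference from SAP 10.2.2.1 and use the Period 1 comparison in SAP 10.2.1.1 as the contrast with placebo. Keep the planned long-term event rates by exposure group.

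If the difference is kept:
- state whether it is pooled or per AESI;
- label it non-randomised and non-concurrent;
- name an interval that does not set placebo variance to zero at zero events, such as a score interval for a rate difference.

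Two optional additions would make the long-term tables more useful: first-event incidence rates per exposure group (exposure censored at first event) with exact Poisson CIs; and, if a long-term contrast is wanted, randomised 15 mg against randomised 30 mg with both arms cut at the same point before the dose switch.

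The cost is SAP wording, a table shell and one descriptive column. No randomised information is lost and no reported Period 1 analysis is reopened, since SAP 11.1 says: "The current SAP update applies only to future reporting of long-term analysis".

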#### **10.2.2.2 Adverse Events Rates per 100 Patient-Years of Study Drug Exposure by SOC and PT**

For each treatment group, the TEAE rate per 100 patient-years of exposure will be calculated overall, for each SOC and each PT, for each of the following events:

- All TEAEs
- Treatment-emergent serious adverse events (SAEs)
- Treatment-emergent severe adverse events
- TEAEs reasonably possibly related to study drug
- TEAEs leading to discontinuation of study drug
- TEAE leading to death

For this calculation, 1 year will be considered to be 365.25 days. For each treatment group, the numerator of the overall rate, the SOC rate, or the PT rate, will be the total number of TEAEs reported overall, for the SOC, or for the PT, respectively; that is a subject can be counted more than once overall, for a SOC, and for a PT. For each treatment group, the denominator of the rates will be the total number of days exposed to study drug summed across all treated subjects divided by 365.25. Please refer to Section 6.0 for the calculation of study drug exposure. The AE rate per 100 patient-years of exposure will be calculated as  $[(\text{numerator}/\text{denominator})]*100$ . The number of AEs reported (numerator), the total number of years of study drug exposure (denominator), and the AE rate per 100 patient-years will be presented overall, for each SOC, and for each PT for each treatment group.

### **10.2.2.3 Adverse Events of Special Interest Rates per 100 Patient-Years of Study Drug Exposure**

The Adverse Events of Special Interest (AESI) categories will be summarized and presented for each treatment group and overall using SOC and MedDRA PT. The AESI categories will be identified as defined in Table 8. Adjudicated cardiovascular events will be summarized and presented by treatment group using the CAC adjudicated categories.

For each treatment group, the Adverse Events of Special Interest (AESI) rate per 100 patient-years of exposure will be calculated overall, for each SOC and each PT, for each of the AESI listed in Section 10.2.1.6.

For this calculation, 1 year will be considered to be 365.25 days. For each treatment group, the numerator of the overall rate, the SOC rate, or the PT rate, will be the total number of TEAEs reported overall, for the SOC, or for the PT, respectively; that is a subject can be counted more than once overall, for a SOC, and for a PT. For each treatment group, the denominator of the rates will be the total number of days exposed to study drug summed across all treated subjects divided by 365.25. Please refer to Section 6.0 for the calculation of study drug exposure. The AE rate per 100 patient-years of exposure will be calculated as  $[(\text{numerator}/\text{denominator})]*100$ . The number of AEs

reported (numerator), the total number of years of study drug exposure (denominator), and the AE rate per 100 patient-years will be presented overall, for each SOC, and for each PT for each treatment group.

**10.2.2.4 Listing of Serious Adverse Events (Including Deaths) and Adverse Events Leading to Study Drug Discontinuation**

All serious adverse events (SAEs), deaths, and adverse events leading to discontinuation of study drug will be listed.

**10.3 Analysis of Laboratory Data**

**10.3.1 Variables and Units**

All laboratory parameters to be collected in this study are listed below. Laboratory parameters will be reported using the standard international (SI) units.

**Table 9. List of Laboratory Variables**

Laboratory Variables
Hematology
White Blood Cell (WBC) Count
Red Blood Cell (RBC) Count
Hemoglobin
Hematocrit
Platelets count
Neutrophils
Basophils
Eosinophils
Lymphocytes
Monocytes
Bands
Chemistry
Total Bilirubin
Alkaline Phosphatase (ALP)
Serum glutamic oxaloacetic transaminase (SGOT/AST)

**Table 9. List of Laboratory Variables (Continued)**

Laboratory Variables
Chemistry (continued)
Serum glutamic pyruvic transaminase (SGPT/ALT)
Total Protein
Albumin
Glucose
Triglycerides
Blood Urea Nitrogen (BUN)
Creatinine
Uric acid
Sodium
Potassium
Calcium
Inorganic Phosphorus
Creatine Phosphokinase (CPK)
Chloride
Bicarbonate
Cholesterol
LDL cholesterol
HDL cholesterol
International Normalized Ratio (INR) reflex only
Urinalysis
Specific Gravity
pH
Protein
Glucose
Ketones
Blood
Microscopic Examination (if needed)
Urobilinogen
Bilirubin
Leukocytes
Nitrites

